# 3.1.1. Screening Period

At screening, the patient will provide a signed informed consent form prior to any study-related activities. Collection and shipment of a formalin-fixed paraffin-embedded (FFPE) tumor sample to the central pathology lab should occur as early as possible, and no later than 8 weeks following Cycle 1 Day 1 (see Section 4.1.1). The tumor sample will be used for central confirmation of EBV status and verification of lymphoma subtype. Additional screening evaluations must be performed within 28 days or 14 days before treatment start as defined in the Schedule of Events (Section 6.1). At the time of screening, patients should be advised around their options to store germ cells.

#### 3.1.2. Treatment Period

Patient eligibility will be confirmed once all screening procedures are completed.

Enrolled patients will receive treatment until disease progression (per Investigator assessment), unacceptable toxicity, withdrawal of consent, Investigator's discretion, death, initiation of new antineoplastic therapy, discontinuation from the study for any reason, or study termination by the Sponsor. Patients receiving nanatinostat monotherapy who have disease progression will be offered the option to receive combination therapy with valganciclovir. All antineoplastic therapies given after the last dose of study drug (and time to next therapy) will be recorded in the electronic case report form (eCRF) (unless the patient withdraws consent or is lost to follow-up). Patients will be followed for survival regardless of treatment discontinuation reason (except if consent is withdrawn or patient is lost to follow-up).

#### 3.1.3. Safety Follow-up Period

Upon discontinuation of the protocol-specified treatments, patients will enter the Follow-up period. All patients will be followed for AEs for 28 days after the last dose of study drug (permanent discontinuation) and complete the Safety Follow-up visit as described in Section 7.2.5, except if the patient is lost to follow-up or withdraws consent (see Section 8.1).

## 3.1.4. Long-term Follow-up Period

In the Long-term Follow-up period, patients will be followed-up as described in Section 7.2.6 (or more frequently if a survival update is required for safety or regulatory reasons) for disease progression, OS, subsequent anti-lymphoma therapies, and response (best overall responses and disease progression date) to subsequent lymphoma therapies. Survival information can be obtained by phone calls, clinic visits, or public records, such as government census or death records, until the patient is lost to follow-up, death, or withdraws consent.

### 3.1.5. Timing of Analyses

Because of the open-label single treatment regimen design elements, each cohort will be monitored individually for safety and efficacy. Therefore, each cohort may move from Stage 1 to Stage 2 and complete Stage 2 at different rates. The decision to expand enrollment will also occur independently for each cohort. However, a study-wide analysis of response and safety over all cohorts will be performed once all cohorts have either discontinued or completed assessments of response at the end of Stage 2 and those with responses have been followed for up to 3 years.

## 3.1.6. End of Study

The end of the study occurs when all patients have either progressed, discontinued, died, become lost to follow-up, or have maintained a CR, PR, or SD for at least 3 years, or when the trial is terminated by the Sponsor.

Patients continuing to derive benefit from study treatment in the opinion of the Investigator at the end of the study may be able to continue receiving study drugs on an individual basis (eg, by separate protocol or post-trial access plan) with Sponsor approval.

### 4. SELECTION OF STUDY POPULATION

Patients must have a histologically confirmed diagnosis of relapsed EBV+ lymphoma, must have been previously treated for their lymphoma with systemic therapy, must be refractory to or have relapsed after their last treatment, must have at least one measurable lesion by computed tomography (CT) or magnetic resonance imaging (MRI) scan, and must have adequate bone marrow function, liver function, and renal function.

The eligibility criteria are designed to limit enrollment to patients who have relapsed/refractory EBV+ lymphoma and who are sufficiently well to safely participate in study procedures and provide interpretable results. Prior therapy provisions are intended to define patient subgroups that have already received available/standard of care therapies with well-defined activities.

# 4.1. Patient Population

#### 4.1.1. Inclusion Criteria

To be eligible for study participation, patients must meet all the following inclusion criteria:

- 1. Adult patients age ≥18 years or as permitted by applicable local regulations at the time of providing informed consent. Patients must be able to swallow whole tablets.
  - a. For patients with PTLD: Age  $\ge 12$  years and weighing  $\ge 40$  kg.
- 2. Histologically confirmed (by 2016 WHO classification (Swerdlow 2016)) EBV+ lymphoma\* per local laboratory by EBER-ISH (or for PTLD only, by LMP-1 immunohistochemistry) on a representative disease specimen. Any degree of EBER-ISH or LMP-1 positivity is considered to be eligible (ie, there is no cut-off value for % positive cells).
  - \* Tumor cells are EBV+, with the exception of AITL, which is characterized by EBV-negative neoplastic T cells and EBV+ associated B-lineage cells (of immunoblastic/plasmablastic immunophenotype)
  - a. A recent FFPE specimen must be available for retrospective central review of diagnosis. FFPE tissue blocks are preferred; if a tissue block is not available, at least 15 unstained slides or freshly cut serial sections (3–5 μm in thickness), preferably with an accompanying block punch will be accepted. The specifications for the age of the tumor samples are:
    - For patients with ENKTL, AITL, PTLD and HIV-L: preferably ≤1 year old. For tumor specimens >1 year old, please consult the Medical Monitor to discuss eligibility.
    - For patients with all other lymphoma subtypes: preferably ≤6 months old. For tumor specimens >6 months old, please consult the Medical Monitor to discuss eligibility.
- 3. **For patients with EBV**+ **DLBCL, NOS:** Relapsed or refractory disease following 1 or more prior systemic therapy(ies) with curative intent. Patients must have received at least one course of an anti-CD20 immunotherapy such as rituximab, and at least one course of anthracycline-based chemotherapy (unless contraindicated, in which case, an accepted anthracycline-free alternative for DLBCL was given).
- 4. **For patients with ENKTL:** Relapsed or refractory disease following 1 or more prior systemic therapy(ies) with a curative intent. Patients must have failed an asparaginase-containing regimen.
- 5. For patients with PTCL (PTCL, NOS and AITL): Relapsed or refractory disease following 2 or more prior systemic therapy(ies) with a curative intent.
- 6. For patients with HL: Patients must have received at least one course of anthracycline-based chemotherapy (unless contraindicated, in which case, an accepted anthracycline-free alternative for HL was given). Patients with relapsed/refractory classical Hodgkin lymphoma(cHL) should have failed or be ineligible for an anti-PD-1 agent (eg, pembrolizumab, nivolumab) and CD30-directed therapy (ie, brentuximab vedotin).

- 7. **For patients with PTLD:** Patients with relapsed or refractory EBV+ PTLD who have received at least one prior therapy must have received at least one course of an anti-CD20 immunotherapy such as rituximab. For solid-organ transplant (SOT) patients, prior therapy also includes chemotherapy, administered concurrently or sequentially, unless chemotherapy is inappropriate.
- 8. For patients with the following lymphomas associated with HIV infection: plasmablastic, Burkitt, Hodgkin, and DLBCL.
  - a. Prior therapy requirements for DLBCL and HL are specified in inclusion criteria 3 and 6.
  - b. **France only:** For Burkitt and plasmablastic lymphoma Patients must have received a regimen such as EPOCH, CODOX-M (original or modified; cyclophosphamide, vincristine, doxorubicin, and high-dose methotrexate) or Hyper-CVAD (cyclophosphamide, vincristine, doxorubicin, and dexamethasone), including CNS prophylaxis or therapy.
- 9. Patients with HIV-L should meet the following criteria for inclusion:
  - a. Currently on a stable regimen of anti-retroviral therapy (ART)
  - b. Compliant with ART and follow-up according to the investigator
  - c. No evidence of a worsening HIV viral load (as assessed by HIV quantitative polymerase chain reaction [qPCR])
  - d. CD4 count >50 cells/mm^3
- 10. No available standard therapies in the opinion of the Investigator.
- 11. Not eligible for high-dose chemotherapy with allogeneic/autologous stem cell transplantation or CAR-T therapy at the time of study entry.
- 12. Presence of at least one bi-dimensionally measurable lesion by CT or MRI: longest diameter (Ldi) >1.5 cm for a nodal lesion; Ldi >1.0 cm for an extranodal lesion within 28 days prior to start of treatment.
- 13. Able to provide a prior core or excisional biopsy for biomarker analysis at screening. If no tissue is available, then a new biopsy must be performed.
- 14. Eastern Cooperative Oncology Group (ECOG) performance status 0, 1, or 2.
- 15. All acute toxic effects of any prior anti-tumor therapy resolved to Grade ≤1 before initiation of study treatment (excluding alopecia and stable Grade 2 sensory neuropathy).

16. Required baseline laboratory data (within 2 weeks prior to start of study drug administration) as shown in the table below:

System	Laboratory Value
Hematology	
Absolute neutrophil count (ANC)	≥1000/mm³ (no growth factor support within 14 days)
Platelets	≥50,000/mm³ (no platelet transfusion within 14 days)
Hemoglobin	≥8.0 g/dL (no red cell transfusion within 21 days)
Renal	
Creatinine clearance	≥50 mL/min (Cockcroft-Gault)
Hepatic	
Total bilirubin	<pre> ≤2.0 × upper limit of normal (ULN) (except patients with documented Gilbert's syndrome [<3.5 × ULN])</pre>
Aspartate aminotransferase (AST [SGOT]) and alanine aminotransferase (ALT [SGPT])	≤3.0 × ULN (or ≤5.0 × ULN if liver involvement by primary disease)
Coagulation	
International normalized ratio (INR) Activated partial thromboplastin time (aPTT)	≤1.5 × ULN unless participant is receiving anticoagulant therapy (as long as INR or aPTT are within the therapeutic range of intended use of anticoagulants)

- 17. Life expectancy > 3 months.
- 18. Women of childbearing potential (ie, reached menarche, and not premenarchal or post-menopausal [no menses for 12 months without an alternative medical cause, or surgically sterile]) must have the following:
  - a. Understand that the study medication is expected to have teratogenic risk.
  - b. Have a negative serum beta human-chorionic gonadotropin ( $\beta$ -hCG) pregnancy test at screening.
  - c. Commit to true abstinence from heterosexual intercourse: When this is in line with the preferred and usual lifestyle of the patient (Periodic abstinence [eg, calendar, ovulation, symptothermal, post-ovulation methods], declaration of abstinence for the duration of exposure to the investigational medicinal product [IMP], or the withdrawal method are not acceptable forms of contraception). Otherwise, begin a highly effective method of birth control with a Pearl-Index <1%, without interruption, throughout the study dosing period and for 6 months after the last dose of nanatinostat. Apart from abstinence, highly effective methods of birth control include the following:
    - Combined (estrogen- and progestogen-containing) hormonal contraception associated with inhibition of ovulation (oral, intravaginal, transdermal). Please note: Although the potential for drug interactions and risk of venous

- thromboembolism is low (see Section 5.5.2.3), the use of an alternative method of contraception is recommended.
- o Progestogen-only hormonal contraception associated with inhibition of ovulation (oral, injectable, implantable).
- o Intrauterine device (IUD).
- o Intrauterine hormone-releasing system (IUS).
- o Bilateral tubal occlusion.
- Vasectomized partner.
- 19. Male patients must agree to use condoms during intercourse throughout the study dosing period and for 90 days after the last dose of nanatinostat. Female partners of male patients participating in the study are to consider the use of effective methods of contraception while their partner is treated on study and for 90 days after the last administration of nanatinostat.
- 20. The patient is willing and able to provide informed consent and comply with the protocol. Assent must be obtained for adolescent patients <18 years old, or as permitted by applicable local regulations, and a parent/guardian must provide written consent.

#### 4.1.2. Exclusion Criteria

Patients meeting any of the following criteria will be excluded from the study:

- 1. Presence or history of central nervous system (CNS) involvement by lymphoma.
- 2. Systemic anticancer therapy within 21 days prior to Cycle 1 Day 1 dosing.
- 3. Antibody (anticancer) agents within 28 days of Cycle 1 Day 1 dosing.
- 4. Less than 14 days from prior local site radiation therapy.
- 5. Less than 60 days from prior autologous hematopoietic stem cell or solid organ transplant.
- 6. Less than 21 days from prior CAR-T therapy (any AEs must be Grade 1 or less for enrollment).
- 7. Less than 90 days from prior allogeneic transplant.
- 8. Receiving systemic corticosteroids during the last week prior to Cycle 1 Day 1, unless administered at a dose equivalent to ≤20 mg/day of prednisone.
- 9. For recipients of prior allogeneic HSCT: Receiving systemic immunosuppressants as either prophylaxis or treatment for graft-versus-host disease (GvHD).
- 10. Major surgery within 28 days within the first dose of study drug. In the case of recent major surgery, the patient must have recovered adequately from the procedure and/or any complications prior to starting study treatment.
  - Note: Minor surgery (eg, minor biopsy of extracranial site, central venous catheter placement, shunt revision) is permitted within 3 weeks prior to enrollment.

- 11. Is currently participating in or has participated in an interventional study of an investigational agent or has used an investigational device within 4 weeks prior to the first dose of study treatment.
  - Note: Individuals who have entered the follow-up phase of an investigational study may participate as long as it has been 4 weeks since the last dose of the previous investigational agent.
- 12. History of other malignancy that could affect compliance with the protocol or interpretation of results. Patients with any malignancy appropriately treated with curative intent and the malignancy has been in remission without treatment for ≥2 years prior to enrollment are eligible. Also eligible are the following:
  - Curatively treated:
    - i. Basal cell, squamous cell carcinoma, or melanoma of the skin (at any time prior to the study).
    - ii. Cervical carcinoma in situ (at any time prior to the study).
  - Low-grade, early-stage prostate cancer (Gleason score 6 or below, Stage 1 or 2) with no requirement for therapy at any time prior to study, or previously fully resected.
- 13. Inability to take oral medication, malabsorption syndrome or any other gastrointestinal condition (nausea, diarrhea, vomiting) that may impact the absorption of nanatinostat and valganciclovir.
- 14. Active GvHD.
- 15. Positive hepatitis B core antibody or surface antigen unless DNA qPCR is negative, and patient will be receiving prophylaxis for reactivation.
- 16. Positive hepatitis C virus on RNA polymerase chain reaction (PCR).
- 17. Known SARS-CoV-2 positivity by any testing method at time of screening. Patients with a positive PCR test should only be enrolled if ≥10 days have passed since COVID symptoms first appeared and they have recovered from symptoms or have mild symptoms.
- 18. History of allergic reactions attributed to compounds of similar chemical or biologic composition to valganciclovir or nanatinostat.
- 19. Active infection requiring systemic therapy (excluding viral upper respiratory tract infections). Patients may be receiving prophylactic antiviral, antifungal or antibacterial therapies at the discretion of the Investigator.
- 20. Prolongation of corrected QT interval using Fridericia's formula (QTcF) to >480 msec, requires the coadministration of drugs known to prolong QT (Class Ia [disopyramide, quinidine, procainamide] and Class III [sotalol, dofetilide, ibutilide] antiarrhythmic agents) (Drew 2010), and/or has a history of Torsades de Pointes (TdP).
- 21. Receiving concomitant drugs that are inhibitors of P-glycoprotein (P-gp) and/or breast cancer resistance protein (BCRP; unless they can be held for 2 weeks or 5 half-lives, whichever is longer), prior to administration of nanatinostat (see Appendix 1).

- 22. Psychiatric illness/social situations/substance abuse disorder that would interfere with compliance with study requirements.
- 23. Has a prior or ongoing clinically significant illness such as New York Heart Association Class III or IV cardiac disease, myocardial infarction within the last 6 months, unstable arrhythmias, or unstable angina, or pulmonary disease, medical condition, physical finding, electrocardiogram (ECG) finding, or laboratory abnormality that, in the Investigator's opinion, could affect the safety of the patient, impair the assessment of study results, interfere with the patient's compliance with the protocol, or is not in the best interest of the patient to participate.
- 24. Is pregnant or breastfeeding or expecting to conceive or father children within the projected duration of the study, starting with the Screening visit through 6 months after the last dose of nanatinostat.

# 5. STUDY TREATMENT PRODUCT INFORMATION

For this study, the term "study treatment" refers to the combination of nanatinostat and valganciclovir, except for those patients enrolled into Cohort 3a (nanatinostat monotherapy for the first 6 weeks).

### 5.1. Nanatinostat

# **5.1.1.** Dosage Form and Composition

Nanatinostat is available as 10 mg tablets. Instructions for requesting and receiving nanatinostat from the Sponsor will be included in the Pharmacy Manual. Nanatinostat will be dosed on a flat scale of mg/day.

Nanatinostat film coated immediate-release (IR) 10 mg tablets consist of the active nanatinostat (VRx-3996), and inactive excipients (ie, mannitol, microcrystalline cellulose, croscarmellose sodium, sodium stearyl fumarate, and coating material).

All inactive ingredients in the drug product meet compendial requirements of the United States Pharmacopeia (USP) and/or National Formulary.

### **5.1.2.** Nanatinostat Study Drug Storage

Nanatinostat should be stored at controlled room temperature (20 to 25°C, 68 to 77°F) in a secure location. Excursions are permitted to 15 to 30°C (59 to 86°F). Once the bottle seal is broken, bottles should be stored tightly capped.

#### **5.1.3.** Nanatinostat Administration

All patients will receive nanatinostat 20 mg orally once daily on Days 1 to 4 per week (ie, 4 days on, 3 days off). Patients will continue dosing in 28-day cycles until discontinuation as described in Section 7.2.3.

There are no special dietary restrictions or requirements associated with nanatinostat, however valganciclovir absorption is affected by food and it should be taken with food (see Section 5.2.2

for additional clarification). Valganciclovir and nanatinostat should be taken at the same time following a light meal.

On study visit days requiring PK trough levels, patients will be asked to consume one can of Ensure® or equivalent or consume a light breakfast in place of consuming an Ensure® equivalent prior to dosing in order to avoid taking study drugs on an empty stomach (see Section 5.3).

See Section 5.5.2 for medications to be used with caution with nanatinostat.

# 5.2. Valganciclovir

Valganciclovir is available as 450 mg tablets. Valganciclovir tablets will be provided to the investigational sites by Viracta. Instructions for requesting and receiving valganciclovir will be included in the Pharmacy Manual. Valganciclovir tablets must not be broken or crushed. Valganciclovir tablets consist of the active valganciclovir hydrochloride, and inactive excipients (ie, microcrystalline cellulose, povidone K-30, crospovidone, magnesium stearate or stearic acid and coating material).

# 5.2.1. Valganciclovir Study Drug Storage

Valganciclovir should be stored at controlled room temperature (20 to 25°C, 68 to 77°F) in a secure location. Excursions are permitted to 15 to 30°C (59 to 86°F). Once the bottle seal is broken, bottles should be stored tightly capped.

# 5.2.2. Valganciclovir Administration

The daily dose of valganciclovir for patients ≥17 years of age is 900 mg orally (continuous treatment) in combination with nanatinostat. Patients with a CrCl 50-59 mL/min at study entry will receive valganciclovir 450 mg orally once daily as per Table 4. Patients will continue to receive nanatinostat plus valganciclovir in 28-day cycles until discontinuation as described in Section 7.2.3.

The daily dose of valganciclovir for patients ≤16 years of age is based on body surface area (BSA) and CrCl derived from a modified Schwartz formula, and is calculated using the equation below:

Adolescent dose (mg) =  $7 \times BSA \times Schwartz$  Creatinine Clearance

$$Mosteller\ BSA\ (m^2) = \sqrt{\frac{Height\ (cm)\ x\ Weight\ (kg)}{3600}}$$
 
$$Schwartz\ Creatinine\ Clearance\ (mL\ /\ min\ /\ 1.73m^2)\ = \frac{k\ x\ Height\ (cm)}{Serum\ Creatinine\ (mg\ /dL)}$$

Note: k value is 0.55 (boys <13 years and girls <16 years) or 0.7 (boys aged 13 to 16 years).

Patients should be monitored for serum creatinine levels regularly, consider changes in height and body weight, and adapt the valganciclovir dose as appropriate. Valganciclovir tablet dose is

determined based on the calculated valganciclovir dose in mg and available tablet strength (450 mg)  $\pm 10\%$  range of the tablet strength. For example, if the calculated dose exceeds 900 mg, a maximum dose of 900 mg should be administered. If the calculated dose is between 900 mg and 810 mg, a 900 mg dose (two 450 mg tablets) should be taken. If the calculated dose is between 809 mg and 405 mg, 450 mg dose (one 450 mg tablet) should be taken.

Adequate hydration should be maintained for all patients. For patients who develop an elevated creatinine while on study, their dose of valganciclovir should be adjusted (see Section 5.4.1).

In patients who are unable to tolerate oral dosing of valganciclovir, the Investigator will have the option of administering ganciclovir intravenously (IV) at 5 mg/kg QD. In patients who are receiving a dose of valganciclovir less than 900 mg orally once daily, the dose of ganciclovir will be reduced accordingly using the ratio of 900 mg valganciclovir to 5 mg/kg ganciclovir.

Valganciclovir absorption is affected by food. Therefore, patients should be instructed to take both valganciclovir and nanatinostat with food and not fasting.

All dosages of study treatment prescribed and dispensed to the patient, and all dose adjustments during the study must be accurately recorded in the eCRFs.

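### Protocol 5.2.2 does not lead to one valganciclovir dose for every eligible adolescent: there is no k for 16-year-old girls, no instruction below 405 mg, and a ±10% wording that does not match the printed bands

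*Protocol*

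**What the plan says.** Section 5.2.2 sets the daily dose for patients aged 16 or younger as 7 × BSA × Schwartz creatinine clearance, with Mosteller BSA and clearance equal to k × height / serum creatinine. The note on the constant says "k value is 0.55 (boys <13 years and girls <16 years) or 0.7 (boys aged 13 to 16 years".

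The tablet dose is then "determined based on the calculated valganciclovir dose in mg and available tablet strength (450 mg"), within a ±10% "range of the tablet strength". The worked bands follow as an example:

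- Above 900 mg: "if the calculated dose exceeds 900 mg, a maximum dose of 900 mg should be administered".
- 810 to 900 mg: two tablets, 900 mg.
- 405 to 809 mg: "If the calculated dose is between 809 mg and 405 mg, 450 mg dose (one 450 mg tablet) should be taken".

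Nothing is said about results below 405 mg.

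Related text:

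- Section 5.2: "Valganciclovir is available as 450 mg tablets", and "Valganciclovir tablets must not be broken or crushed". Only 0, 450 or 900 mg can therefore be given on a day within the 900 mg cap.
- Section 5.4.1: patients aged 12 to 16 whose creatinine rises on study have clearance recalculated by the formula in 5.2.2 and the dose adjusted. Patients aged 17 or older use Table 4, which has steps down to a clearance below 10 mL/min.
- Section 4.1.1: PTLD patients may enter from age 12 at 40 kg or more, with no restriction by sex (criterion 1a). Creatinine clearance must be at least 50 mL/min by Cockcroft-Gault (criterion 16).

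**The concern.** A dosing rule should give each eligible patient one answer. Here three pieces of text do not fit together: the age and sex scope against the k note, the tablet bands against the low end of the calculated dose, and the ±10% phrase against its own example.

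The patients concerned are adolescents in the PTLD cohort, which is not among the cohorts closed to enrollment. If a site has to supply its own k or its own rule for a low result, two sites may treat like patients differently. Renal function is where this bites. Section 1.3.2 lists renal dysfunction as an overlapping toxicity of the two drugs, and Section 1.2.4 reports increased blood creatinine in 17 of 64 patients (26.6%) in the earlier study. Section 5.2.2 also scales intravenous ganciclovir from the patient's oral dose, so a gap in the oral dose carries over.

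The stakes are exposure and safety in a small group. The primary endpoint, alpha, power and decision rules are not affected.

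**Working it through.** **1. The ±10% phrase against the printed bands (all inputs from Section 5.2.2).**

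- One tablet: 0.9 × 450 = 405 mg; 1.1 × 450 = 495 mg.
- Two tablets: 0.9 × 900 = 810 mg; 1.1 × 900 = 990 mg.

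The printed lower limits, 405 and 810 mg, are reproduced exactly as minus 10%. The printed upper limit of the one-tablet band, 809 mg, is not: plus 10% gives 495 mg. Results of 496 to 809 mg lie outside both ±10% windows.

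Side by side:

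| Calculated dose (mg) | ±10% phrase | Printed band |
|---|---|---|
| below 405 | none | none |
| 405–495 | 450 | 450 |
| 496–809 | none | 450 |
| 810–900 | 900 | 900 |
| above 900 | 900 up to 990, then none | 900 (cap) |

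No row has two different doses.

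**2. The missing k.** Ages covered by the formula: 16 or younger. k is given for boys under 13 and girls under 16 (0.55), and for boys 13 to 16 (0.7). Girls aged 16 are inside the formula and outside the note. Section 5.4.1 only refers back to 5.2.2, and SAP Section 4.6.4 describes only Cockcroft-Gault, so no other text supplies the value.

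Size of the choice: 0.7 / 0.55 = 1.27, or 27% in the calculated dose.

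Illustration (assumed, not from the documents): girl aged 16, 160 cm, 50 kg, creatinine 1.2 mg/dL.

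- Eligibility: 0.85 × (140 − 16) × 50 / (72 × 1.2) = 61 mL/min, above 50.
- BSA = √(160 × 50 / 3600) = 1.491 m².
- k = 0.55: clearance 0.55 × 160 / 1.2 = 73.3; dose 7 × 1.491 × 73.3 = 765 mg; dispensed 450 mg.
- k = 0.7: clearance 0.7 × 160 / 1.2 = 93.3; dose 7 × 1.491 × 93.3 = 974 mg; dispensed 900 mg.

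Range over which this happens: the calculated dose is 7 × 1.491 × 160 × k / creatinine, or about 1,670 × k / creatinine. It reaches 810 mg at creatinine 1,670 × 0.55 / 810 = 1.13 with the lower k and 1,670 × 0.7 / 810 = 1.44 with the higher. Between about 1.14 and 1.44 mg/dL the dispensed dose differs twofold. Her eligibility limit is 0.85 × 124 × 50 / (72 × 50) = 1.46 mg/dL, so the range lies inside eligible values. Elsewhere within those values both k give the same tablet count.

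**3. Results below 405 mg.** The Schwartz clearance at which the calculated dose is 405 mg is 405 / (7 × BSA). Assumed body sizes:

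- 150 cm, 40 kg (BSA 1.291): 44.8 mL/min/1.73 m².
- 160 cm, 50 kg (BSA 1.491): 38.8.
- 165 cm, 60 kg (BSA 1.658): 34.9.

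Below these values no tablet dose is stated. For example, at 150 cm and 40 kg with creatinine 2.0 mg/dL and k = 0.55, clearance is 0.55 × 150 / 2.0 = 41.2 and the dose is 7 × 1.291 × 41.2 = 373 mg.

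Can this occur at entry? Take a boy of 12 at 140 cm with the highest creatinine that still gives a Cockcroft-Gault value of 50.

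- 50 kg: creatinine 128 × 50 / (72 × 50) = 1.78; BSA 1.394; clearance 0.55 × 140 / 1.78 = 43.3; dose about 423 mg.
- 60 kg: creatinine 128 × 60 / (72 × 50) = 2.13; BSA 1.528; clearance 36.1; dose about 386 mg.

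Over assumed heights of 140 to 170 cm and weights of 40 to 100 kg, entry doses below 405 mg appear only from 60 kg upward, mostly at 80 to 100 kg, and with creatinine above 2 mg/dL. The gap is therefore mainly an on-study one.

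**The case against.** A reader might infer that the ±10% phrase and the bands send sites to different doses, and that patients in the 496 to 809 mg range lose between 9% and 44% of their dose because of it (450/496 = 91%, 450/809 = 56%). The documents do not support that. For 496 to 809 mg the ±10% phrase gives no dose at all, and the band gives one. Tablets may not be split, so the shortfall comes from rounding down with a single 450 mg strength. It would be the same if the phrase were reworded to fit the bands. The bands are also coherent as a one-sided rule, moving up only when the result is within 10% below the next whole-tablet dose. The protocol does not state that rule, but the example behaves as if it did. This part of the objection stands in full.

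On k, the objection is that this is an omission rather than a contradiction, covers one year of age in one sex and one cohort, and usually leaves the tablet count unchanged. Section 7.1.8 also has each registration approved by the sponsor's chief medical officer or a designee, which gives a site a chance to ask. All of that is fair and limits the size. It does not close the gap, because the approval step supplies no value and Section 5.4.1 calls for the same formula again after enrollment.

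On doses below 405 mg, the objection that they are remote at entry holds. It does not reach the on-study case.

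Few adolescents may be enrolled. SAP Section 4.6.2 makes their separate adverse event summaries conditional on at least 5 patients.

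**Conclusion.** The point holds as two missing instructions and one wording inconsistency.

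- **No k for 16-year-old girls.** The dose cannot be calculated as written. The printed k values differ by 27%, with a twofold difference in dispensed dose (450 against 900 mg) over a limited creatinine range, about 1.14 to 1.44 mg/dL for the assumed 160 cm, 50 kg girl. Other body sizes would shift that range.
- **No instruction below 405 mg.** It is reachable mainly when creatinine rises on study, at Schwartz clearances below about 35 to 45 mL/min/1.73 m² for the three assumed body sizes.
- **±10% against the bands.** 405 to 495 mg against 405 to 809 mg. This is a mismatch of wording only, since the bands give one answer from 405 mg upward.

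Heights, weights and creatinine values are illustrative assumptions. No view is taken on which k, band or dose is right.

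**What to change.** Revise Section 5.2.2 so that three pairs of statements agree:

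- the age and sex scope of the formula with the k note;
- the ±10% wording with the printed bands;
- the range below 405 mg with the instruction in Section 5.4.1 to recalculate when creatinine rises.

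The test of the revision is that every eligible age, sex and calculated dose leads to exactly one instruction. The sponsor's clinical team must decide what each instruction says, and any intravenous ganciclovir dose scaled from it should be checked at the same time.

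The cost is a protocol clarification of one section, with a cross-check of Section 5.4.1. Sample size and analyses do not change.
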